
 
• Concordance between investigator's intra-operative conspicuity assessment of the ureter and BICR assessment for adults with normal renal function or mild renal impairment
 
	
 
• Intra-participant difference in ureter conspicuity for WL versus NIR-F at 30 (<math>\pm 15</math>) min after ASP5354 administration by each BICR reader
 
• CCC, the inter-rater reliability between the investigators and BICR for the WL versus NIR-F at 30 (<math>\pm 15</math>) min after ASP5354 administration
 
• Intra-participant difference in ureter conspicuity for WL at 30 (<math>\pm 15</math>) min versus the average of all NIR-F time points by each BICR reader
 
• CCC, the inter-rater reliability between the investigators and BICR for the WL at 30 (<math>\pm 15</math>) min time point versus the average of all NIR-F time points
 
• Intra-participant difference in ureter conspicuity for WL at 30 (<math>\pm 15</math>) min versus the
 

Objectives	Endpoints
	
end of surgery time point score with NIR-F by each BICR reader
 
 
CCC, the inter-rater reliability between the investigators and BICR for the WL 30 (<math>\pm</math> 15) min time point versus the end of surgery time point score with NIR-F
 

 
Safety of ASP5354
 
	
 
Nature, frequency, severity and causality of TEAEs and serious TEAEs
 
Clinical laboratory tests (hematology, biochemistry and urinalysis)
 
Vital signs
 
Electrocardiograms/cardiac monitoring
 

 
Investigate the pharmacokinetics of ASP5354
 
	
 
Plasma and urine concentrations of ASP5354
 
Ae and Ae%
 

Exploratory	

 
To summarize the investigator's conspicuity assessment with WL of the ureter at each time point
 
	
 
Descriptive summary of left and right ureter conspicuity scores for WL at each time point
 
Descriptive summary of index and non-index ureter conspicuity scores for WL at each time point
 

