6.4.2 Analysis of Key Secondary Efficacy Endpoints

The population used for the analysis of key secondary endpoints will be the ITT population. Adolescent and moderate/severe renally impaired participants that are enrolled directly into the WL/NIR-F arm will not be included in the analysis of the key secondary endpoints.

The first key secondary endpoint of the 30-min time point WL conspicuity score versus the mean NIR-F conspicuity score across all time points will be analyzed using a sign test which will test if the median of the intra-participant time point difference means between the NIR-F score at each time point and the 30-min WL score is equal to 0. Prior to the analysis, the conspicuity scores will be windowed to time points every 30 minutes per the algorithm in Section 6.8.1.

The value used in the sign test for each participant will be derived as follows. The differences between the NIR-F scores at each time point and the 30-min WL score will be calculated for each participant. The mean of these differences will then be calculated for each participant. A sign test will be conducted using these mean differences to test if the median of the intra-

participant time point difference means between the NIR-F scores and 30-min WL scores is equal to 0.

Prior to the sign test, participants who experience ICE1 or ICE2 will have their 30-min conspicuity data imputed using the same algorithm as described in section [6.4.1.1](#).

Additionally, the following imputation rules will be applied to NIR-F conspicuity scores at other time points after 30-min prior to the sign test.

- Participants who experience ICE1 will have NIR-F conspicuity scores at time points after ICE1 set as their WL conspicuity assessment at the 30-min time point.
- Participants who are unable to have NIR-F conspicuity scores assessed by the investigator at time points after 30-min will have such NIR-F scores left as missing.

If a participant does not have a conspicuity assessment at a time point due to the surgery ending before the time point, the time point will be left as missing prior to the sign test.

The following results will be presented:

- For comparisons between WL and NIR-F:
 - Frequency and percentage of participants with a positive mean difference, negative mean difference and mean difference of 0.
 - Summary statistics of the mean differences between 30-min WL and NIR-F time points.

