The analysis of the additional secondary endpoints will be conducted using the following groups of participants. P-values and confidence intervals will not be presented. This analysis will be performed after applying the ICE1 and ICE2 imputation as well as the visit windowing algorithm described in section [6.8.1](#).

- Adolescents
- Adults with moderate renal impairment (eGFR ≥ 30 to < 60 mL/min)
- Adults with severe renal impairment (eGFR ≥ 15 to < 30 mL/min)

To further characterize the difference of ureter conspicuity under NIR-F vs WL, the frequency and percentage of participants with an averaged ureter conspicuity assessed by the investigator over all NIR-F time points during surgery at least 1 point higher than the average ureter conspicuity over all WL time points during surgery will be presented. The same analysis will be repeated using a difference of 2, 3 and 4 points. The frequency and percentage of participants with an averaged ureter conspicuity within NIR-F during surgery at least 1 point higher than their WL conspicuity at the 30-min time point during surgery will be presented. The analysis will also be repeated using a difference of at least 2, 3 and 4 points.

The qualitative assessment of index ureter(s) conspicuity scored on a 5-point Likert Scale under WL and NIR-F (1 = None, 2 = Poor, 3 = Sufficient, 4 = Good and 5 = Excellent) performed by a BICR will be summarized descriptively at all time points post-ASP5354 administration by WL and NIR-F for each separate BICR reader. The descriptive analysis of the primary and key secondary endpoints will be repeated for each separate BICR reader. This analysis will be conducted within adolescents, adults with moderate renal impairment, adults with severe renal impairment, the ITT population and the mITT population. The BICR data will be assigned to the same analysis time points as the corresponding investigator assessments. The same ICE1 and ICE2 imputation will also be applied within the BICR data. In the event that a BICR assessment cannot be collected for a corresponding investigator assessment, the corresponding analysis time point will be considered missing in the BICR analysis. If a backup reader is utilized in place of a primary reader, the primary reader and their backup will be considered the same BICR reader in the analysis.

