The concordance analysis between BICR readers and investigators will be conducted for the ITT population. The hypothesis testing for the primary and key secondary endpoints will be repeated for each separate BICR reader. This will be the primary measure of concordance between the BICR readers and investigator data. A high concordance between the two assessments is considered if 2 of 3 BICR readers yield p-value ≤ 0.05 .

The CCC measuring the agreement between investigator and BICR Likert conspicuity scores will be presented for the following values for each separate BICR reader for the ITT population. This is considered a secondary measure of reliability compared to the hypothesis testing as differences between the raw conspicuity scores of the BICR readers and investigator data may be expected due to the different environments under which conspicuity is assessed.

- Difference between NIR-F and WL at the 30-min time point
- Mean difference between NIR-F across all time points and WL at the 30-min time point
- Difference between NIR-F at the end of surgery time point and WL at the 30-min time point

In addition to the CCC, Kendall's coefficient of concordance along with 95% jackknife CI will be presented in order to assess the agreement across all raters.

BICR data will be listed.

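### SAP 6.4.3 drops an uncollectable BICR time point on the reader's side only, so the investigator–reader CCC for the average of all NIR-F time points can compare means over different time points

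*Protocol*

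**What the plan says.** Protocol Table 4 and Protocol 9.3.3.2 define three CCCs between the investigator and each BICR reader. The second is "CCC, the inter-rater reliability between the investigators and BICR for the WL at 30" min versus the average of all NIR-F time points. Neither place says what happens when a reader has no usable image.

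The rules are in the SAP:

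- SAP 6.4.2 builds the value for one participant: "The differences between the NIR-F scores at each time point and the 30-min WL score will be calculated for each participant", and those differences are then averaged. If the investigator could not score NIR-F at a time point after 30 min, the participant "will have such NIR-F scores left as missing".
- SAP 6.4.3 lists the CCC input for each reader as "Mean difference between NIR-F across all time points and WL at the 30-min time point".
- On alignment, SAP 6.4.3 says: "The BICR data will be assigned to the same analysis time points as the corresponding investigator assessments".
- On imputation, it says: "The same ICE1 and ICE2 imputation will also be applied within the BICR data".
- Where a BICR assessment cannot be collected, "the corresponding analysis time point will be considered missing in the BICR analysis".
- On the role of the CCC: "This is considered a secondary measure of reliability compared to the hypothesis testing". High concordance is declared when 2 of 3 readers reach p ≤ 0.05.

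**The concern.** A CCC is a paired statistic, and it falls with scatter between the two raters and with any shift between their means. For the all-time-point average, each member of the pair is itself a mean over time points. If an image is unavailable, the reader's mean loses that time point. The investigator's mean keeps it, because no sentence takes it out. Sharing time-point labels does not make the two sets of time points equal.

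The coefficient then reflects which images could be read as well as how they were rated. This matters because the 2-of-3 rule asks whether each reader finds a nonzero difference, not whether the scores agree. The CCC and Kendall's coefficient are the planned checks of score-level agreement between investigator and BICR. The SAP already attributes expected score differences to the different assessment environments, and an artefact of unmatched time points could be mistaken for that cause.

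**Working it through.** **No figure to reproduce.** The documents state no CCC value, target or missing-image rate. Everything below on missing images is assumed.

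**One participant.** WL at 30 min is 2, and the investigator's NIR-F scores are 5, 5, 4, 3, 2. The reader gives identical scores on the first three images and has no image for the last two.

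- Investigator: (5+5+4+3+2)/5 − 2 = 3.80 − 2 = 1.80
- Reader: (5+5+4)/3 − 2 = 4.67 − 2 = 2.67
- Gap: 0.87 points, with full agreement on every shared image
- On shared time points only: 2.67 against 2.67, gap 0

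The example is deliberately unfavourable, because exactly the two lowest scores are lost.

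**Number of participants for the illustration.** From Protocol 9.5.1.1 (SD 2.0, correlation 0.2), the SD of the difference is √(2 × 2.0² × (1 − 0.2)) = 2.530. For a mean difference of 1.0, the paired t-test has 89.9% power at n = 69 and 90.3% at n = 70. The allocation ratio is not stated. A 5:1 ratio would put 84 × 5/6 = 70 in the WL/NIR-F arm, so 70 is used as an assumption.

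**Reader identical on every shared image.** CCC = 2·cov/(var₁ + var₂ + (mean₁ − mean₂)²). Assumed: 2 to 7 time points, integer scores 1 to 5, mean NIR-F 4.0 and mean WL 2.3 before rounding, 30-min image always present, three settings for score spread and trend, 200 runs each. The table gives the range of mean CCC across the three settings.

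| Loss setting | At random | More often when score ≤ 3 |
|---|---|---|
| 0% | 1.000 | 1.000 |
| 10% | 0.985–0.997 | 0.975–0.997 |
| 20% | 0.968–0.994 | 0.942–0.993 |
| 30% | 0.947–0.990 | 0.894–0.987 |
| 50% | 0.894–0.980 | 0.736–0.970 |

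In the last column an image scored 3 or lower is lost at twice the setting, and any other at half. When the later half of the images is lost in 10% to 30% of participants, the range is 0.960–0.998. At 10% to 30% random loss, 22% to 57% of participants had unequal means despite full agreement. On shared time points the CCC was 1.000 throughout.

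**With rater noise** (70 participants, 2 to 7 time points, participant SD 0.7, time SD 1.0, rater SD 0.5):

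| Loss | As planned | Matched | Gap |
|---|---|---|---|
| None | 0.778 | 0.778 | 0 |
| 30% at random | 0.749 | 0.777 | 0.028 |
| Weighted to late time points | 0.723 | 0.754 | 0.031 |
| Weighted to low visibility | 0.710 | 0.748 | 0.038 |

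**How the gap depends on variation over time.** A variant with continuous scores, no WL term and random loss gives, planned against matched:

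| Time SD | 10% loss | 30% loss |
|---|---|---|
| 1.0 | 0.886 v 0.908 | 0.819 v 0.893 |
| 0.5 | 0.876 v 0.879 | 0.838 v 0.847 |
| 0.3 | 0.870 v 0.865 | 0.845 v 0.831 |

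The largest gap is 0.893 − 0.819 = 0.074. It comes from omitting the WL term, whose variation does not depend on which NIR-F images exist and so dilutes the loss in the real endpoint. At time SD 0.3 the sign reverses, because matching averages rater noise over fewer investigator scores.

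**The case against.** The strongest reply is that little depends on this. The CCC has no threshold, lies outside the H1 to H3 sequence and does not enter the 2-of-3 rule. Only one of the three CCCs uses the average. Video is recorded throughout surgery and images are prepared from it with investigator timestamps, so loss may be rare. All of that stands and limits the point to a minor one.

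It can also be said that missing in the BICR analysis covers the concordance comparison, which sits in the same section, so that the time point is dropped on both sides. The wording allows that reading but does not state it. Two programmers could reach different CCCs, which is itself a reason to clarify.

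Two stronger readings are tempting, and the documents do not support them:

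- A reader might infer that a BICR reader who agrees on every shared image will be scored as disagreeing. With complete images nothing happens. With missing images the means differ only if the omitted scores average differently from those kept, and at moderate random loss the coefficient stays near 1.
- A reader might infer that poorly visible ureters drop out and push the readers' means upward. The scale has a score for that case, 1 = None, so an available image with an invisible ureter is scored low. No document links uncollectable assessments to visibility or to late time points.

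Nor is the investigator's mean over literally every time point, since unassessed NIR-F scores are left missing.

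**Conclusion.** The mechanism holds as a matter of text: the reader's time point is dropped, and no sentence drops the investigator's. For the all-time-point average, the CCC can fall below 1 through image availability alone.

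The size is small under plausible loss. For a fully agreeing reader the mean CCC is about 0.95 to 1.00 at 10% to 30% loss that is random or late in surgery. With rater noise the change is typically about 0.03 or less, and it vanishes or slightly reverses when scores vary little over time. It becomes material only with heavy or score-dependent loss (0.894 at worst at the 30% setting, 0.736 at 50%). These figures rest on assumed loss rates and score spreads.

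A related ambiguity reaches all three CCCs. SAP 6.4.3 applies ICE2 imputation to BICR data and also calls an uncollected BICR time point missing. It is therefore unclear whether a missing 30-min reading is filled from a later image or left missing. If filled, the reader's 30-min value would come from a different moment than the investigator's.

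This is a worthwhile clarification of a secondary reliability measure. It does not affect the primary or key secondary conclusions.

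**What to change.** In SAP 6.4.3:

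1. For each reader, compute the CCC values for both raters over only those time points, NIR-F and the 30-min WL, that were scored by both the investigator and that reader.
2. Compute Kendall's coefficient over time points scored by all raters. It spans all raters, and matching reader by reader could give the investigator up to three different means.
3. State whether ICE2 imputation fills a missing 30-min BICR reading or the reading stays missing.
4. Report the number of matched and unmatched time points per reader.
5. Keep the CCC on all available time points as a supportive result.

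The cost is a few sentences and a merge step in the program. There is a small downside. Matched means use fewer investigator scores, so the CCC may be slightly noisier, and they depart from the literal average of all NIR-F time points in Table 4. That is why the all-available version should be retained. The investigator's full-surgery mean still serves H2, and H1 to H3 and the 2-of-3 rule do not change.

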### 3.1 Primary Estimands

#### Population:

Male and female participants  $\geq$  18 years of age with eGFR  $\geq$  60 mL/min undergoing minimally invasive and open abdominopelvic surgeries. The population is further defined by the eligibility criteria.

**Treatment Regimen:**

The treatment regimen is ASP5354, 1 single intravenous dose of 3 mg (3 [three] 1 mg vials).

**Primary Endpoint:**

Intra-participant difference in ureter conspicuity for WL versus NIR-F at the 30-min time point after ASP5354 administration. The first assessment will always be under WL followed by NIR-F assessment. Conspicuity will be scored individually for each illumination mode using the 5-Point Likert Scale.

**Intercurrent Events (ICEs) and Strategies:**

*ICE1:* Participants who have received the medications or therapy listed below within 48 hours prior to ASP5354 administration and/or before the completion of the surgical procedure:

- ICG, unless used for anastomotic evaluation after the ureters have been visualized or for lymphatic mapping where there is a clear anatomic separation of the ureters and the lymphatics
- Other NIR-F imaging agents
- Ureteral stent

*Composite strategy for ICE1:* The assessment of ureter conspicuity after ICE1 will not be considered as relevant and will be handled as missing data. For participants that experience ICE1 prior to the 30-min time point conspicuity assessment by the investigator, both conspicuity values at the 30-min time point with WL and NIR-F will be set as '1 = Not self-evident' for the primary endpoint analysis.

*ICE2:* Participants who are unable to have ureter conspicuity assessed by the investigator at the 30-min time point for any reason.

*Treatment policy strategy for ICE2:* The assessment of ureter conspicuity in the event of ICE2 will be imputed as follows. In the event that WL or NIR-F conspicuity is not assessed by the investigator at the 30-min time point, the first collected conspicuity assessment under the respective illumination mode will be used as the 30-min time point value. If a participant does not have any assessments under a respective illumination mode during the entire surgery, the 30-min time point value will be set as the 30-min value from the other illumination mode. If a participant does not have any assessments under either illumination mode during the entire surgery, both 30-min time point values will be set as '1 = Not self-evident'.

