## **5.2 Exclusion Criteria**

Participant will be excluded from participation in the study if any of the following apply:

1. Participant has any physical or psychiatric condition, which, in the investigator's opinion, makes the participant unsuitable for study participation.
2. Participant is anticipated to require ureteral stenting during surgery.
3. Participant has an active urinary tract infection requiring antibiotic therapy.
4. Participant has moderate to severe cardiac disease that limits daily functioning (New York Heart Association Class III to IV) or other medical conditions that the investigator feels would impact safety or study compliance.
5. Participant has any clinically relevant laboratory abnormality that could contraindicate surgery in the opinion of the investigator.
6. Participant with body weight < 30 kg.
7. Participant has a known or suspected hypersensitivity to ASP5354, ICG or any components of the formulation used.
8. Participant has had previous exposure to ASP5354.
9. Participant has been administered ICG or other NIR-F imaging agents within 48-hours prior to ASP5354 administration, with the exception of participants who receive ICG for lymphatic mapping before the surgery.
10. Participant has received any investigational therapy within 28 days or 5 half-lives, whichever is longer, prior to randomization.
11. Participant is on hemodialysis, hemodiafiltration or peritoneal dialysis

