## 6.8 Prior and Concomitant Therapy

The following concomitant medications listed below will not be allowed within 48 hours prior to ASP5354 administration through the completion of the surgical procedure:

- ICG unless used for anastomotic evaluation after the ureters have been visualized or for lymphatic mapping where there is a clear anatomic separation of the ureters and the lymphatics
- Other NIR-F imaging agents

Participants anticipated to require ureteral stents during surgery are excluded from the study [Exclusion Criterion No.2]. Ureteral stents however may be used based on clinical judgment of the investigator during surgery. Diuretics should be avoided 48-hours prior to ASP5354 administration until the completion of the surgical procedure but can be used based on clinical judgment of the anesthesiologist or investigator.

A list of excluded concomitant medications is provided in [Section 10.5].

Concomitant and corrective treatments (medication and non-medication therapy) will be recorded in the eCRF. However, there is no need to record supplements, nutrients or intravenous solutions for hydration.

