### 9.3.1 General Considerations

In general, data will be summarized with descriptive statistics for continuous endpoints, and frequency and percentage for categorical endpoints, unless otherwise specified. Percentages by categories will be based on the number of participants with no missing data (i.e., will add up to 100%). Baseline will be defined as the last non-missing observation prior to administration of study intervention, unless otherwise specified.

Efficacy summaries for the primary and key secondary endpoints will be presented for all participants in the Intent to Treat (ITT) population which includes all participants in the adult normal/mild eGFR cohort randomized to WL/NIR-F. Efficacy data collected for adult

participants randomized to the WL-only arm will be listed only. Efficacy summaries for the adolescent and adult moderate/severe eGFR cohort will be presented as other secondary analyses.

Unless otherwise specified, efficacy analyses will use data from one ureter for each participant based on selection by the investigator. If the investigator selects either the left or right ureter as the ureter of interest before surgery, then data from the selected ureter will be used in the efficacy analyses. If the investigator selects both ureters as ureters of interest, the index ureter selected by the investigator (either left or right) will be used in the efficacy analyses.

Unless otherwise specified, all safety summaries will be presented by arm and for all participants in the Safety Analysis Set (SAF). More specifically, safety summaries will be presented for the following groups of participants unless otherwise specified:

- All participants who receive ASP5354
- Adult participants ( $\geq 18$  years of age)
- Adult participants randomized to the WL/NIR-F arm
- Adult participants randomized to the WL-only arm
- All participants enrolled/randomized to the WL/NIR-F arm
- Adolescent participants ( $\geq 12$  to  $< 18$  years of age)
- Moderate renal impairment participants ( $eGFR \geq 30$  to  $< 60$  mL/min)
- Severe renal impairment participants ( $eGFR \geq 15$  to  $< 30$  mL/min)

Additional subgroups for safety summaries may be considered based on feasibility. Details will be given in the SAP.

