5 ANALYSIS ENDPOINTS

5.1 Primary Efficacy Endpoint

The primary efficacy endpoint is the intra-participant difference in ureter conspicuity for WL versus NIR-F at the 30-min time point after ASP5354 administration. Conspicuity will be scored individually for each illumination mode using the 5-Point Likert Scale.

Primary Estimand

Population:

Male and female participants \geq 18 years of age and eGFR \geq 60 mL/min undergoing minimally invasive or open abdominopelvic surgeries. The population is further defined by the eligibility criteria.

Treatment Regimen:

The treatment regimen is ASP5354, 1 single dose of 3 mg.

Primary Endpoint:

Intra-participant difference in ureter conspicuity for WL versus NIR-F at the 30-min time point after ASP5354 administration. Conspicuity will be scored individually for each illumination mode using the 5-Point Likert Scale.

Intercurrent Events (ICEs) and Strategies:

ICE1: Participants who have received the medications or therapy listed below within 48 hours prior to ASP5354 administration and/or before the completion of the surgical procedure:

- Indocyanine green (ICG), unless used for anastomotic evaluation after the ureters have been visualized or for lymphatic mapping where there is a clear anatomic separation of the ureters and the lymphatics.
- Other NIR-F imaging agents
- Ureteral stent

Composite strategy for ICE1: The assessment of ureter conspicuity after ICE1 will not be considered as relevant and will be handled as missing data. For participants that experience ICE1 prior to the 30-min time point conspicuity assessment by the investigator, both conspicuity values at the 30-min time point under WL and NIR-F will be set as ‘1 = Not self-evident’ for the primary endpoint analysis.

ICE2: Participants who are unable to have ureter conspicuity assessed by the investigator at the 30-min time point for any reason.

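### ICE1 counts a ureteral stent per participant with no side, so a stent in the other ureter overwrites scores observed on the analysed ureter

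*Protocol*

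**What the plan says.** - **Definition.** Protocol 3.1 defines ICE1 as "Participants who have received the medications or therapy listed below within 48 hours prior to ASP5354 administration", and the sentence runs on, so the full window is "within 48 hours prior to ASP5354 administration and/or before the completion of the surgical procedure". Three items follow: ICG, other NIR-F agents, and "Ureteral stent". ICG carries exemptions, one of them resting on anatomic separation. The stent entry has no qualifier: no side, and no condition that it is still in place. SAP 5.1 and the ICE table in SAP 6.4.5 repeat the list.
- **Primary endpoint.** SAP 5.1 states: "The assessment of ureter conspicuity after ICE1 will not be considered as relevant and will be handled as missing data". If ICE1 comes before the 30-min assessment, both 30-min scores are set to 1.
- **Key secondary endpoints.** Under SAP 6.4.2, participants with ICE1 "will have NIR-F conspicuity scores at time points after ICE1 set as their WL conspicuity assessment" from 30 min. Protocol 9.3.3.1 has the same rule.
- **Other data.** SAP 6.4.3 applies the ICE1 imputation to the blinded independent central review (BICR) scores and sets color contrast to 1 for images taken after ICE1.
- **Unit of analysis.** Unless otherwise specified, "efficacy analyses will use data from one ureter for each participant based on selection by the investigator" (protocol 9.3.1; also SAP 6.1). If both ureters are of interest, the index ureter is used.
- **Stents in the trial.** Exclusion criterion 2 reads: "Participant is anticipated to require ureteral stenting during surgery". Protocol 6.8 adds: "Ureteral stents however may be used based on clinical judgment of the investigator during surgery".

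**The concern.** An intravenous dye can reach both ureters, so a participant-level flag suits it. A stent sits in one ureter. Because the flag has no side and the analysis uses one ureter, a stent on the side that is not analysed discards scores that were observed on an unstented ureter and were the target of the estimand. At stake are the three tested hypotheses (H1, H2, H3), the BICR and color-contrast analyses that inherit the rule, and the ICE table, whose single stent row cannot tell the two situations apart.

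**Working it through.** **1. What happens to a contralateral stent.** Suppose the right ureter is the index ureter and the left is stented during surgery.

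- Stent before the 30-min assessment: WL and NIR-F at 30 min both become 1, so the H1 difference is 1 − 1 = 0. Later NIR-F scores are set to the 30-min WL score, so H2 and H3 are also 0.
- Stent at 70 min, with observed WL 2 at 30 min and NIR-F 5 at end of surgery: the end-of-surgery score becomes 2, and H3 records 2 − 2 = 0 instead of 5 − 2 = +3. In H2 the time points after the stent contribute 0. The sign test uses only the sign of the participant's mean difference, so it loses the participant mainly when all differences become 0.

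**2. Timing condition.** Protocol 3.1 and SAP 5.1 set the 30-min scores to 1 only if ICE1 precedes that assessment. Protocol 9.3.2.1 and 9.3.3.1 and SAP 6.4.1.1 state the same imputation for anyone with ICE1, without that condition. Read literally, the stent at 70 min would also zero H1, although the 30-min pair was already scored. SAP 6.8.1 points the other way, to data after ICE1. The literal reading has a side effect in H2: a NIR-F score of 5 observed at 60 min would be compared with a WL score reset to 1, giving 4 instead of 3. The passages must be reconciled. The sizes below use the 3.1 condition.

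**3. The time window.** For a stent placed more than 48 hours before dosing and still in place, there are two readings. The limb after the and/or has no lower bound, so taken alone it captures any earlier stent. Read as one closed window, as protocol 6.8 words it for the imaging agents, it does not. The wording turns on when the therapy was received, not on whether a stent is in the analysed ureter when it is scored.

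**4. Size.** Inputs from protocol 9.5.1.1: mean difference 1.0, common SD 2.0, correlation 0.2, two-sided 0.05, 90% power, 84 randomized.

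- SD of the difference = 2.0 × √(2 × (1 − 0.2)) = 2.530.
- Normal approximation: n = 68. Exact paired t-test: n = 70, power 90.3%.
- The plan's 84 gives 84 × 5/6 = 70 in the WL/NIR-F arm at an assumed 5:1. At 4:1 it gives 67 (89.0%), at 6:1 72 (91.1%), at 3:1 63 (87.1%) and at 1:1 42 (70.6%). The plan's figure therefore reproduces at about 4:1 to 6:1.
- One overwritten participant moves the mean by that participant's own difference divided by 70: 1/70 = 0.014, 3/70 = 0.043, and at most 4/70 = 0.057.
- With k participants overwritten and q = k/70: mean = 1.0 × (1 − q), variance = (1 − q) × 2.530² + q(1 − q) × 1.0².

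| Assumed k | Mean | Power for H1 |
|---|---|---|
| 0 | 1.000 | 90.3% |
| 1 | 0.986 | 89.9% |
| 3 | 0.957 | 88.9% |
| 7 | 0.900 | 86.6% |

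A simulation with k fixed (100,000 runs) gives 90.0%, 89.2% and 87.2% for k = 1, 3 and 7.

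**The case against.** The strongest reply is that 3.1 declares a composite strategy at participant level: the event itself counts as an unfavourable result, and an analysis on one ureter does not oblige every intercurrent event to be ureter-specific. The rule works against the product when NIR-F is better. Anticipated stenting is excluded, so only unplanned stents on the other side matter, and they may be few. Stent cases will also be visible: SAP 6.4.5 plans an ICE table with a stent row, an ICE listing, a swimmer plot, and score summaries by time point without imputation. On timing, protocol 9.3.2.1 refers back to 3.1, so the condition there may be intended throughout.

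The points on direction, likely rarity and visibility stand. The composite argument does not settle the matter. Nothing in the plan explains why a stent in the unanalysed ureter should count as a failure of visualization in the analysed one, and the ICG exemption shows that the plan already treats anatomy as relevant. The unimputed summaries are descriptive. The sensitivity analysis in protocol 9.3.2.2 and SAP 6.4.1.2 removes the imputed zeros, but it uses the same flag, so it does not bring the observed scores back.

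A reader might go further and infer that a stent placed days earlier and still in the analysed ureter escapes ICE1, so that stents are misclassified in both directions. The documents do not support that. The second limb of the window can be read to include such a stent, and no passage describes such a participant. Exclusion criterion 2 does not name indwelling stents, though it may keep some out.

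**Conclusion.** The point holds for side. As written, a stent in the other ureter replaces valid index-ureter scores with zero differences, and no planned test recovers them. The timing condition is inconsistent between the estimand and analysis sections. Capture of an earlier indwelling stent is ambiguous, not shown to be absent.

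The effect is small unless such stents are common: 0.014 per participant at the design mean, at most 0.057, and about 1.4 points of H1 power for three cases (90.3 − 88.9). This assumes about 70 analysed, which needs an allocation ratio near 5:1 that the documents do not state, and an assumed number of stents, because frequency and side are not given. Under the 3.1 timing condition the direction is toward zero. A reader might infer type I error inflation, but replacing observed differences with zeros does not produce it. The case for change is that the rule overwrites valid data and leaves the estimand loosely defined, not that it threatens the trial's conclusion.

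**What to change.** These are changes to analysis wording only; care is unaffected.

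- In protocol 3.1 and SAP 5.1, separate the stent from the imaging agents. Keep the existing window for the agents. Define the stent component as a stent present in the analysed ureter at the time of the assessment, whenever it was placed.
- Apply the ICE1 imputation for Likert, BICR and color-contrast data only to those assessments. Keep observed index-ureter scores when the stent is only on the other side.
- Show other-side stents as a separate row in the SAP 6.4.5 ICE table.
- Carry the 3.1 timing condition into protocol 9.3.2.1 and 9.3.3.1 and SAP 6.4.1.1, consistent with SAP 6.8.1.
- Take side and time of the stent from the non-medication therapy records or, where missing, from the surgery video. State in advance how a stent of unknown side is handled, for example by keeping the present rule for it.

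The cost is a small data check and slightly more programming. The eCRF is not among the documents, so side and time may already be recorded. If they are not, new prospective fields may come too late, because SAP 4.0 is dated 17 February 2025 and the planned study period ended in 4Q2024. The video helps only with stents placed during the recorded surgery.
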